7.2. Calculation of Sample Size

7.2.1. Total Sample Size

The primary endpoint of the study is the success rate of recanalization, using non-inferiority test. A total of 220 patients are planned to be enrolled and randomly assigned to the test or control group in a 1:1 ratio, with 110 subjects in each group. mTICI can reach 76% at 6-16h according to DEFUSE-3 and 84% at 6-24h according to DAWN. Within 6 h, mTICI is 86% in EXTEND-IA, 88% in SWIFT PRIME, and 87% in PISTE.

According to the estimation combined with the existing clinical evidence and the experience of clinical experts, assuming that the recanalization success rate after treatment is 89% in both the test group and control group within 24h ^[10-19], the non-inferiority margin is set at 12.5% after discussion between the clinical investigator and the sponsor. When the significance level α of statistical test is set as one-sided 0.025 and the power $1-\beta$ is set as 80%, the sample size is calculated as 99 in each group. In consideration of the maximum possible dropout rate of 10% in the study, the sample size in each group is 110. Therefore, 220 subjects are required in total. It is calculated according to statistical principles that,

the corresponding sample size formula is:

$$n_T = n_C = \frac{(Z_{1-\alpha/2} + Z_{1-\beta})^2 [P_C(1 - P_C) + P_T(1 - P_T)]}{(|D| - \Delta)^2}$$

where, n_T and n_C are the respective sample size of the test group and control group; $Z_{1-\alpha/2}$ and $Z_{1-\beta}$ are the percentiles in standard normal distribution; P_T is the expected success rate of recanalization in the test group, P_C is the expected success rate of recanalization in the control group; $|D|$ is the absolute value of the

difference between groups in the expected recanalization, $|D| = |P_T - P_C|$; Δ is the non-inferiority margin (taking the negative value).

7.2.2. Number of Subjects for Each Disease and Rationale for Determination

In this trial protocol, the inclusion/exclusion criteria for selected patients are strictly limited. It can be considered that the current study is only conducted for patients with a single indication. The above 220 patients have the same disease and are no longer further divided.

7.2.3. Minimum and Maximum Number of Subjects in Each Site and Justification

This trial will be carried out at the same time in multiple study sites. In principle, the number of subjects enrolled in each site will be distributed as evenly as possible to ensure adequate site representation. However, considering the feasibility and progress of the selection, the number of subjects enrolled in each participating site will be adjusted according to the actual situation, so as to ensure that the enrollment scale at each site is relatively balanced, and that the final enrollment scale for a specific site should not exceed 50% of the total number of cases.

8. Significance Level and Power of Clinical Study

8.1. Expected Drop-out Rate

In determining the sample size, the highest possible drop-out rate during the study is expected to be 10%, including all conditions that make the subjects ultimately excluded from the primary analysis, often referring to major deviation of trial protocol (affecting the primary efficacy evaluation and/or safety evaluation) adjudicated by principal investigator.

It may include the following conditions:

- a) Subjects who, for whatever reason, are unwilling or unable to continue the clinical trial, propose withdrawal from the clinical trial to the investigator and terminate the clinical trial;
- b) Subjects who are lost to follow-up despite not specifically proposing withdrawal from the clinical study but no longer receiving treatment and examination;
- c) Subjects, who experience SAE, should be withdrawn from the clinical study as judged by the investigator;
- d) Subjects, due to poor compliance, fail to complete follow-up for primary outcome;
- e) Lost to follow-up (The investigator cannot reach the subject to return to the

clinic for visit assessment and examination via telephone or mail for two consecutive times).

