6.1.5.3. Criteria and Procedures for Withdrawal from/Discontinuation of Trial Treatment

The subjects may withdraw from the study at any time during the course of the study without giving a reason: moreover, subjects may choose not to undergo any study procedures after signing the ICF, and if subjects choose not to undergo any study procedures after signing the ICF, the investigator must be informed. However, subjects have the right to continue receiving the standard of care regardless of the cases.

Any subject may also be withdrawn from the study by the investigator based on medical judgement.

Subject's premature discontinuation or withdrawal from the study can be any of the following cases, but not limited to:

- 1) The subject is unwilling to continue participating in this study for any reason;
- 2) For medical or safety reasons, the investigator believes that the subject should be withdrawn from the study;
- 3) Serious protocol violation (confirmed by the principal investigator);
- 4) The investigator or the sponsor requests to terminate the study for any reason;
or
- 5) Death.

For all subjects who terminate the study early, the investigator should make every effort to find out the reasons for withdrawal from the trial, for example: adverse

events, failure of corrective treatment, the investigator's decision or other reasons. The reasons for withdrawal should be recorded in the EDC. Subjects who withdraw early should be requested to complete an early withdrawal visit according to the visit schedule.

Subjects who withdraw from the study will not be replaced, i.e. the randomization number will be uniquely related to each subject and cannot be reused.

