6.1.7. Safety Evaluation Methods

6.1.7.1. Description of Safety Endpoints

1) Safety Endpoints

- Safety endpoints: Incidence of symptomatic intracranial hemorrhage within 24 h postoperatively, mortality within 90d, incidence of SAE, incidence of AE, and incidence of device defects.
- #### **2) Selection of Method and Time to Evaluate, Record and Analyze the Safety Endpoints**
- **Incidence of symptomatic intracranial hemorrhage within 24h**

Recording time and method: Symptomatic intracranial hemorrhage within 24h, specifically refers to intracranial hemorrhage (parenchymal hematoma, subarachnoid hemorrhage, ventricular hemorrhage) accompanied by neurological deterioration (NIHSS score increases by ≥ 4 compared with that preoperatively).

Incidence of symptomatic intracranial hemorrhage within 24 h = Number of subjects who develop symptomatic intracranial hemorrhage on CT or MR within 24 h in this group/Number of subjects who receive revascularization device for thrombectomy in this group $\times 100\%$.

* Subjects with symptomatic intracranial hemorrhage postoperatively who show additional hemorrhage on CT or MR within 24 h postoperatively will not be re-evaluated.

● All-cause mortality within 90 days

Recording time and method: Throughout the clinical trial. All-cause mortality = Number of deaths in this group/Number of subjects who receive revascularization device for proximal thrombectomy in this group $\times 100\%$.

● Incidence of device defects

Recording time and method: During the thrombectomy. Incidence of device defects = Number of defective devices / Total number of devices $\times 100\%$.

Note: The investigational device defects that occur during the clinical trial, such as device fracture and mislabeling.

● Incidence of SAE

Recording time and method: Throughout the clinical trial. Incidence of SAE = Number of subjects with SAE/Number of subjects treated with intracranial thrombectomy device for thrombectomy in total $\times 100\%$.

● Incidence of AE

Recording time and method: Throughout the clinical trial, incidence of AE = Number of subjects with AE/Number of subjects who receive intracranial thrombectomy device for thrombectomy $\times 100\%$.

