- 6) Premature termination of visit

Subjects can withdraw from the study at any time, and once a subject withdraws prematurely from the study before the end of the follow-up period, an premature termination visit must be completed as soon as possible and the reason for termination will be recorded. Evaluations to be performed during this follow-up

period is the same as Visit 5. All information will be analyzed and documented by the investigator.

Study Flowchart

Data Collection:

Visit time Visit contents	Screening/Baseline period	Treatment period	Observation period	Follow-up period	
	Preoperatively -1 d ~ 0 d	Day of operation/0 d	Postoperatively 24 h \pm 12 h	Postoperatively 7 d \pm 2 d	Postoperatively 90 d \pm 14 d
Signing of ICF	×				
Medical history	×				
Preoperative diagnosis	×				
Vital signs ¹	×		×	×	
NIHSS score ²	×		×	×	
mRS score ³	×				×
Laboratory test ⁴	×		×		
Pregnancy test ⁵	×				
Cerebral CT or MR ^{6,7}	×		×		
Cerebrovascular DSA ⁷	×				
Verification of eligibility criteria		×			
Randomization		×			
Operations		×			
Antiplatelet and anticoagulant medication	×	×	×	×	×
Adverse event		×	×	×	×
Device defect		×			

Note:

- 1) Vital signs include heart rate and blood pressure.
- 2) NIHSS score: assessing the degree of neurological impairment of the subject.
- 3) MRS score: assessing the degree of disability of the subject.
- 4) Laboratory tests (The laboratory test results at 24 h preoperatively are accepted during the screening period, and one laboratory test within 9d postoperatively is sufficient):

Blood routine: Red blood cell, hemoglobin, white blood cell count, and platelet count

Blood chemistry: Urea nitrogen (urea), serum creatinine, blood glucose

Coagulation: Prothrombin time, activated partial thromboplastin time and

INR

- 5) Only for women of childbearing potential who are planning to become pregnant, blood or urine pregnancy test result is acceptable.
- 6) Cerebral CT or MR is performed when the onset time is ≤ 6 h; cerebral CT or MR is performed when the onset time is 6 (exclusive)-24h (inclusive) to determine whether ASPECTS score ≥ 6 is met; (if immediate CT perfusion imaging or MR perfusion imaging is feasible, CTP or MRP is recommended to assist in the assessment of the infarct core to determine whether ASPECTS score ≥ 6 is met).
- 7) CT or MRI images and DSA images during thrombectomy are burned on a CD in DICOM format and evaluated by a central interpretation room.

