10.2. Possibility Analysis on Failure

The main reasons for failure or poor results may be related to the following factors: 1) The product is seen very special device defects. 2) Too many subjects dropped out due to the development of SAEs. 3) The training for the personnel of the study site is not in place, and the use of the device is not skilled, with the result that the effectiveness of the product fails to meet the requirements.

In addition to the above reasons, there are other unpredictable risks that may exist in this study, leading to its failure. But the risk may be minimized by adherence to this protocol, treatment in the prescribed study sites, compliance with the inclusion/exclusion criteria of the subjects, and close monitoring of the physical condition of the subjects during the treatment or follow-up period.

11. Quality Control of Clinical Trial

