6.1. Subject Distribution

Table1 Case distribution across centers

Center ID	Research Center	Group	Number			
			EnrollmentCount	Dropout Rate (%)	Dropout of ExclusionsRate (%)	Completed
01		Experimental group				
		Control Group				
		Total				
02		Experimental Group				
		Control Group				
		Total				
03		Experimental Group				
		Control Group				
		Total				
.....		Experimental Group				
		Control Group				
		Total				
Total		Experimental Group				
		Control Group				
		Total				

Note 1: Number of completers = Number enrolled - Number of dropouts.

Note 2: Exclusion refers to subjects who completed the trial but were not included in the PPS set.

Table2 Population Distribution by Center

Research Hospital	FAS		PPS		SS		Total
	Center	Experimental group	Control group	Experimental group	Control Group	Experimental group	
01							
02							
03							
.....							
Total							

Table3 Enrolled Cases and Safety/Efficacy Analysis Dataset

Item	Indicator	Experimental Group	Control Group	Total
Reasons for Randomly Assigned				
Early Withdrawal	Completed Trial			
	Adverse events			
	Unsatisfactory treatment response			
	Subject withdrawal of informed consent			
	Protocol violation			
	Other			
	Subject or family member requests withdrawal from the study			
	Loss to follow-up			
	Death			
	Total			
FAS				
PPS				
SS				

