6.7.3. Adverse Events

Table35 Summary of Adverse Events

Item	Experimental Group (n=)		Control Group (n=)		Total (n=)	
	Number of Occurrence	Incidence Rate (%)	Number of Occurrence	Incidence Rate (%)	Number of Occurrence	Incidence Rate (%)
Adverse Event						
Mild adverse events						
Moderate adverse events						
Severe adverse events						
Adverse events related to the investigational device						
Adverse events leading to subject withdrawal from the trial						
Adverse events resulting in death						

Note: Definition of trial device-related adverse events: Adverse events classified as "definitely related," "probably related," "possibly related," or "unclassifiable" to the trial device.

Table36 Summary of Serious Adverse Events

Item	Treatment Group (n=)			Control group (n=)			Total (n=)		
	Occurrence	Number of Subjects	Incidence Rate (%)	Occurrence	Number of Cases	Incidence Rate (%)	Number of cases	Incidence Rate (%)	P value
Serious Adverse Events related to the investigational device									
Serious adverse events resulting in death									

Note: Definition of serious adverse events related to the investigational device: Serious adverse events determined to be "definitely related," "probably related," "possibly related," or "unclassifiable" to the investigational device.

Table37 Event Coding

Item	Experimental Group (n=)			Control Group (n=)			Total (n=)		
	Occurrence	Number of Subjects	Incidence Rate (%)	Occurrence	Number of Cases	Incidence Rate (%)	Number of cases	Incidence Rate (%)	P value
Adverse Event									
SOC1									
PT1									
PT2									
.....									
SOC2									
.....									

Table38 Serious Adverse Event Codes

Item	Experimental Group (n=)			Control Group (n=)			Total (n=)		
	Occurrence	Number of Subjects	Incidence Rate (%)	Occurrence	Number of Cases	Incidence Rate (%)	Number of cases	Incidence Rate (%)	P value
Serious Adverse Events									
SOC1									
PT1									
PT2									

	Experimental Group (n=)	Control Group (n=)	Total (n=)	
Item	Number of Occurrence Subjects	Incidence Rate (%)	Number of Cases	Incidence Rate (%)
.....				
SOC2				
.....				

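### Investigator-initiated withdrawal after an SAE, on safety grounds or for a protocol violation ends study follow-up, and nothing requires day-90 vital status or mRS afterwards

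*Protocol*

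**What the plan says.** Protocol section 6.2.1 places the whole intervention on day 0. The later visits (24 hours, 7 days, 90 days) are follow-up.

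The grounds for leaving are stated at study level:
- Section 8.1, among the drop-out conditions: "Subjects, who experience SAE, should be withdrawn from the clinical study as judged by the investigator".
- Section 6.1.5.3: "For medical or safety reasons, the investigator believes that the subject should be withdrawn from the study", and "Serious protocol violation (confirmed by the principal investigator").

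Other text treats this as a live route. Section 10.2 lists among the possible causes of failure: "Too many subjects dropped out due to the development of SAEs". SAP Table 3 (section 6.1) has early-withdrawal rows for adverse events and for "Protocol violation", and SAP Table 35 has a row for "Adverse events leading to subject withdrawal from the trial".

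After withdrawal, section 6.2.1.3 says that "an premature termination visit must be completed as soon as possible", with the same content as Visit 5 (mRS, medication, adverse events). Section 13.1.3 has recorded adverse events followed until they resolve or the trial ends.

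For analysis, section 6.1.7.1 gives "All-cause mortality = Number of deaths in this group/Number of subjects who receive revascularization device" and so on, that is, known deaths over all treated subjects. SAP section 4 imputes only the primary endpoint in the FAS. Secondary and safety data are left missing.

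**The concern.** Once the device is out, there is no study treatment left to stop. Withdrawal from the study therefore ends observation only. The plan does not distinguish leaving trial procedures from leaving follow-up.

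The grounds listed are tied to prognosis: someone withdrawn after a serious event is more likely than average to die before day 90. The decision rests with an investigator who receives the allocation and uses the assigned device (section 6.2.1.2). The only blinding described is the central image reading (section 6.1.2). Missing outcomes that arise this way are informative, and their number can differ by arm.

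At stake are 90-day all-cause mortality, a named safety endpoint, and 90-day mRS, a named secondary endpoint. The pass/fail rule in section 8.2 also requires the absence of unacceptable device-related safety problems, and mortality is part of the evidence for that judgement.

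**Working it through.** **Plan's own figure.** With 89% success in both arms, a 12.5-point margin, one-sided alpha 0.025 and 80% power (section 7.2.1):

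n = (1.960 + 0.842)² × (2 × 0.89 × 0.11) / 0.125² = 7.85 × 0.1958 / 0.015625 ≈ 98.4, so 99 per arm. Then 99 / (1 − 0.10) = 110. Both stated figures reproduce. The 10% allowance is 11 of 110 per arm and covers all drop-out reasons in section 8.1.

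**What is collected after withdrawal.**
- Already recorded: the triggering event, and mRS and adverse events up to the termination visit.
- Possibly recorded: the outcome of an adverse event already on file, under section 13.1.3. That section does not say whether it applies after withdrawal.
- Not required anywhere: death from another cause, a new SAE, vital status at day 90, mRS at day 90.

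**Effect on 90-day mortality.** Let w be the number withdrawn per arm and r the share of them who die later unseen. Under the all-treated denominator the understatement is w × r / 110. The values of w below the ceiling and the range r = 30-50% are assumptions, because the documents give neither.

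| w of 110 | r = 30% | r = 50% |
|---|---|---|
| 3 | 0.9/110 = 0.8 points | 1.5/110 = 1.4 points |
| 6 | 1.8/110 = 1.6 points | 3.0/110 = 2.7 points |
| 11 (ceiling) | 3.3/110 = 3.0 points | 5.5/110 = 5.0 points |

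For scale, section 4 quotes 3-month mortality of up to 9.6% in hospitalised patients, which would be 0.096 × 110 = 10.6 deaths per arm. That is background text, not a design input. At the ceiling a true 9.6% would be reported as (10.56 − 3.3)/110 = 6.6% to (10.56 − 5.5)/110 = 4.6%.

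**If the SAP tables drop missing subjects instead.** SAP Table 34 has a missing count, so the denominator may be 110 − w. At the ceiling the reported rate is (10.56 − 3.3)/99 = 7.3% to (10.56 − 5.5)/99 = 5.1%. The understatement is smaller but remains.

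**Difference between arms.** With the same r, the spurious shift is (difference in w) × r / 110. A difference of 3 withdrawals gives 0.8-1.4 points in favour of the arm that withdraws more. The documents give no basis for expecting any particular imbalance.

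**Other endpoints.**
- SAE incidence is the number of subjects with an SAE (section 6.1.7.1). A subject withdrawn for an SAE is already in the numerator.
- The mRS proportion divides by all treated subjects (section 6.1.6), so a missing day-90 score counts as not 0-2. SAP Table 29 also has a missing count, so the denominator in use is not settled.
- Recanalisation is read during the procedure (section 6.1.6), before any later withdrawal.

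**The case against.** The case for leaving the text alone has real substance, and several stronger readings that a reader might infer do not survive it.

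- **That every SAE leads to withdrawal.** It does not. Section 8.1 lists conditions that may occur and leaves the decision to the investigator's judgement. Violations need confirmation by the principal investigator. The SAP rows are reporting categories, not rules.
- **That a patient who bleeds on day 1, is withdrawn on day 2 and dies on day 10 is necessarily lost.** The haemorrhage is a recorded event, and section 13.1.3 has it followed. If the death is its outcome, it should be captured, and section 13.4 requires data on any death to be supplied. What stands is that section 13.1.3 is silent on withdrawn subjects, allows follow-up to stop when the event resolves, and does not reach deaths from other causes or the day-90 mRS.
- **That SAE incidence is lowered by SAE-driven withdrawal.** It is counted per subject, so it is not. Only a subject withdrawn without a previous SAE, such as some protocol violators, could have a first SAE missed.
- **That lost mRS scores flatter the arm with more withdrawals.** Under the Protocol formula they count against it.
- **That 3-5 points is the likely size.** It is a ceiling. The 10% also covers consent withdrawal, loss to follow-up, non-compliance and major deviations.

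It is also fair to say that a shift of 1-2 points is small against sampling error. At 9.6% mortality the 95% half-width for the difference is 1.96 × √(2 × 0.096 × 0.904 / 110) ≈ 7.8 points. But a systematic understatement is not reflected in that interval, and it is avoidable.

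**Conclusion.** The point holds in limited form. The stated rules allow discretionary, unblinded, outcome-related withdrawal from follow-up after a one-off procedure, with no required day-90 contact. Under the Protocol's mortality formula an unseen later death is counted as survival. Mortality at 90 days can be understated, possibly unequally by arm, and the day-90 mRS is lost.

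The size is 0.8-1.4 points with 3 of 110 withdrawn, rising to an upper bound of 3-5 points if the entire drop-out allowance were withdrawals of this kind. Both ranges rest on an assumed 30-50% unseen mortality among those withdrawn.

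A reader might infer that the main non-inferiority result is compromised. The documents do not support that: the FAS primary result is little affected, and section 8.2 sets no numerical mortality threshold. There is one side effect: the PPS requires study completion (section 8.6), so a withdrawn subject's observed recanalisation result may drop out of the PPS analysis.

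This should be fixed, but it does not by itself undermine the trial.

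**What to change.** State in sections 6.1.5.3, 6.2.1.3 and 8.1 that a treated subject withdrawn by the investigator for an SAE, on safety grounds or for a protocol violation leaves trial procedures only. Vital status, SAE and mRS collection then continues to day 90 unless the subject withdraws consent or contact is truly lost. Visit 5 already allows telephone follow-up.

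Also:
- say in section 13.1.3 that follow-up of recorded events applies after such a withdrawal;
- handle protocol violations through the analysis sets, not by ending follow-up;
- state in the SAP which denominator applies to mortality and mRS when day-90 status is unknown, and add a sensitivity analysis for subjects with unknown status.

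The investigator's safety discretion over procedures is unchanged. The cost is Protocol and SAP wording and a few extra telephone contacts. The sample size stays at 110 per arm.

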8.2. Pass/Fail Criteria for Clinical Trial Results

If the lower limit of the 95% CI of the difference in recanalization success rate between the test group and control group is greater than -12.5% (the pre-specified non-inferiority margin), and there are no clinically unacceptable safety issues related to the investigational device, the study is qualified, otherwise it is unqualified.

